#### 5.3.4 Examination of Subgroups

Subgroup analyses will be conducted for FL cohort.

For primary efficacy analysis based on the independent reviewer assessment, results will be summarized by subgroups defined by sex (Male/ Female), age group (<65/  $\geq$ 65) and categories of previous chemotherapy(Bendamustine(Y/N), CHOP(Y/N), Rituximab(Y/N)), and lines of prior therapies(= $\leq$ 2/3=, 2= $\leq$ 3= $\leq$ 4=) in order to assess whether the treatment effects are consistent across different subgroups. ORR, its corresponding 2-sided exact 90% confidence intervals (CIs) and 95% CIs using the method of Clopper–Pearson will be calculated. Additional subgroup analyses may also be conducted, if deemed appropriate.

### 5.3.5 Handling of Missing Data, Dropouts, and Outliers

No imputation will be performed for missing data.

Data exceptions will be identified before data base lock based on discussion with medical experts if necessary.

## 5.4 Efficacy Analyses

All efficacy result will be summarized by disease (cohort) and overall. Results from central assessment by Efficacy and Safety Evaluation Committee and investigator assessment will be used.

### 5.4.1 Primary Efficacy Analyses

BOR will be summarized. The rate of subjects whose BOR is CR or PR is calculated as ORR, and its corresponding 2-sided exact 90% confidence intervals (CIs) using the method of Clopper–Pearson will also be calculated. A waterfall plot will be presented for the percent changes from baseline in the sum of the product of diameters of target lesions at post-baseline nadir. Also, percent change from baseline over time will be presented using spider plot. Regarding the ORR, 95% CIs will also be calculated.

### 5.4.2 Secondary Efficacy Analyses

- Analysis of PFS

PFS will be summarized by Kaplan-Meier method using median with 95%CI. Kaplan-Meier curve will be provided. The number of event/censor (percentage) and reasons of censor will be also summarized.

- Analysis of DOR

DOR will be summarized by Kaplan-Meier method using median with 95% CI in responders. The number of event/censor (percentage) and reasons of censor will be also summarized.

- Analysis of TTR

TTR will be summarized using descriptive statistics in responders.

PFS will be calculated as:

End date for PFS – Date of administration of the first dose of study drug + 1 (day)

DOOR will be calculated as:

End date for DOOR – Date of the first response + 1 (day)

End date of PFS and DOOR is defined as the table below:

Situation	End Date for PFS and DOOR	Censored
Documented progression disease (PD) during the study	Date of the first assessment of the series of the tests that determined PD	No
Death during the study before PD	Date of death	No
No baseline assessments	Date of administration of the first dose of study drug	Yes
Treatment discontinuation without post-baseline tumor assessments	Date of administration of the first dose of study drug	Yes
Treatment discontinuation without documented PD or death with post-baseline tumor assessments	Date of last tumor assessment before discontinuation	Yes
New anticancer treatment started prior to disease progression	Date of last tumor assessment before start of new treatment	Yes
Death or PD after more than one missed tumor assessments	Date of the last tumor assessment before missed assessments	Yes
Subjects still on treatment without PD as of data cut-off	Date of last tumor assessment	Yes

TTR will be calculated as:

Date of first response – Date of administration of the first dose of study drug + 1 (day)

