9.1.1.3 Follow-up Phase

Follow-up Phase consists of the evaluation at discontinuation which is performed within 7 days after the discontinuation of the study and a final observation which occurs 30 days (+7 days) after final administration of tazemetostat or initiation of a new anti-tumor therapy, whichever occurs early. Final observation is unnecessary for subjects who withdraw from the study and continuously take commercial tazemetostat.

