9.5.1.3 Efficacy Assessments

Efficacy assessment will be performed by investigator or subinvestigator based on "Revised response criteria for malignant lymphoma (IWG-2007)" (Cheson, et al., 2007). Overall response and best overall response (BOR) (best response recorded at the designated visits during the study) will be assessed. Perform the assessment below for tumor assessment.

CT scans will be performed at Screening 2, every 8 weeks from study drug administration up to first 32 weeks, then every 12 weeks and at discontinuation.

Eisai Confidential Page 42 of 71 FINAL: 29 Jan 2021

PET scans will be performed at Screening 2. If positive, perform when it is required to confirm CR as soon as possible or when clinically indicated.

If gastrointestinal disease is suspected, endoscopic examination will be performed at Screening 2. If exists, perform when it is required to confirm CR as soon as possible or when clinically indicated.

To evaluate bone marrow infiltration, a bone marrow aspiration or biopsy will be performed at Screening 2. If positive or indeterminate, perform when it is required to confirm CR as soon as possible or when clinically indicated.

Also, central review will be conducted by the Imaging Review Committee for CT and PET assessment. In addition, Efficacy and Safety Evaluation Committee (ESEC) will conduct central evaluation based on the review of Imaging Review Committee and other assessment / bone marrow infiltration evaluated by the investigator or subinvestigator, to determine the overall responses and the best overall response.

The primary endpoint and the secondary endpoint with regard to efficacy are defined as below, and will be evaluated by the result of ESEC review.

ORR:

The rate of subjects whose BOR is CR or PR.

PFS

Defined as the term between the date of administration of the first dose of the study drug and the date of the first event (PD or death whichever occurs first). The detail of the censoring rule for PFS will be described in the statistical analysis plan (SAP).

• DOR:

Defined as the term between the date of confirmation of the first response and the date of confirmation of the PD. The detail of the censoring rule for DOR will be described in the SAP.

TTR·

Defined as the term between the date of administration of the first dose of the study drug and the date of confirmation of the first response.

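### Censoring at the last scan before discontinuation can drop a non-PD discontinuation CT from PFS and DOR, and can make DOR negative

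*SAP*

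**What the plan says.** SAP 5.4.2 calculates PFS as end date minus first-dose date plus 1, and DOR (printed there as DOOR) as end date minus first-response date plus 1. One table supplies the end date for both. Four rows matter here:

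- The row "Documented progression disease (PD) during the study" is an event, dated "Date of the first assessment of the series of the tests that determined PD".
- Treatment discontinuation without PD or death, with post-baseline scans, is censored at the "Date of last tumor assessment before discontinuation".
- "Treatment discontinuation without post-baseline tumor assessments" is censored at first dose.
- New anticancer treatment before PD is censored at the last scan before that treatment.

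The table gives no order of precedence and no date definition of discontinuation.

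Protocol 9.5.1.3 schedules CT every 8 weeks to Week 32, "then every 12 weeks and at discontinuation". Table 5 marks the discontinuation scan as required rather than conditional. Protocol 9.1.1.3 describes an "evaluation at discontinuation which is performed within 7 days after the discontinuation of the study". Footnote f of Table 5 lets a scan from the previous 28 days serve as the discontinuation scan.

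**The concern.** A CT taken in the days after stopping is a study assessment, because the discontinuation visit belongs to the Follow-up Phase, one of the study's three phases (protocol 9.1.1). If it shows PD, the PD row makes it an event on that date. If it shows no PD, the discontinuation row goes back to an earlier scan. Whether the scan sets the end date therefore depends on its result, and the asymmetry runs against the drug.

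Two things are at stake. Progression-free follow-up already collected is discarded. And the formulas can return impossible durations, which would force an unplanned decision once the data are in hand. PFS and DOR are secondary endpoints in cohorts planned at 8 and 13 evaluable subjects, so one subject is 1/8 = 12.5% or 1/13 = 7.7% of a cohort, and a larger share of the responders on whom DOR rests.

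**Working it through.** The documents state no figure for this rule, so there is none to reproduce. The check puts dates allowed by the protocol into the SAP formulas.

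**Inputs.** Discontinuation evaluation 0 to 7 days after discontinuation (protocol 9.1.1.3). Screening 2 no more than 28 days before first dose (9.1.1.1). Scan windows from Table 5, footnote f, using study day = (cycle - 1) × 28 + cycle day: C2D21 to C3D7 is Day 49 to 63, C4D21 to C5D7 is Day 105 to 119, C8D21 is Day 217, and C12D7 is Day 315.

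**1. Follow-up lost.** The loss is the gap from the previous scan to the discontinuation CT.
- Nominal gap between scans: up to 56 days, or 84 days after Week 32.
- Extreme, 8-week phase: previous scan Day 49, stop Day 118, CT Day 125; 125 - 49 = 76 days.
- Extreme, 12-week phase: previous scan Day 217, stop Day 314, CT Day 321; 321 - 217 = 104 days.

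**2. Response first seen on the discontinuation CT.** That CT starts DOR but cannot end it, so DOR = 1 - gap.
- Stop Day 91, PR on Day 95, previous scan Day 57: 57 - 95 + 1 = -37 days. The Day 57 scan is 34 days before stopping, so the 28-day reuse option is not available.
- Nominal gaps of 56 and 84 days give -55 and -83 days.

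**3. Response seen earlier and still present at stopping.** First response Day 57, stop Day 91, non-PD CT Day 95. Under the row as written, DOR = 57 - 57 + 1 = 1 day, censored. With the CT counted, it is 95 - 57 + 1 = 39 days, censored.

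**4. Discontinuation CT is the only post-baseline scan.** The subject can enter the Efficacy Analysis Set (SAP 5.2.1) because a post-baseline assessment exists. Under the discontinuation row, the last earlier scan is the Screening 2 scan:

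| Screening scan, days before first dose | PFS (days) |
|---|---|
| 28 | -28 + 1 = -27 |
| 14 | -14 + 1 = -13 |
| 1 | -1 + 1 = 0 |

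If the row for no post-baseline assessments is applied instead, PFS = 1 day. The table does not say which row governs.

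**5. Size across a cohort.** This needs assumptions that the documents do not give. In a simulation with median PFS of 6 or 12 months and 15% to 30% stopping for other reasons by 12 months, 6% to 19% of patients were affected. Each lost a median of 6 to 7 weeks, and 6- and 12-month PFS moved by less than 1 percentage point.

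**6. After the fix.** Case 2 becomes 95 - 95 + 1 = 1 day, censored. In case 4, a stop on Day 31 is censored between Day 31 and Day 38, according to when the CT is done. No non-positive time remains in these cases.

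**The case against.** A reader might infer that the discontinuation CT is always discarded unless it shows PD. The documents do not support that. A scan from the previous 28 days may serve as the discontinuation scan; if it precedes discontinuation, it is kept and nothing is lost. The new-treatment row can also keep the CT. The CT still counts for BOR, ORR and TTR, so the primary endpoint does not change.

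A reader might also infer that PFS must come out negative after an early stop. That requires letting the discontinuation CT admit the subject to the row for those with post-baseline scans, then ignoring it for the date. Applying the other row gives 1 day, a valid censored time. This part is a conflict between rows, not a certain negative value.

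Discontinuation is also undefined. Protocol 9.1.1.3 speaks of discontinuing the study, whereas the SAP row speaks of treatment discontinuation. If study exit is meant, the CT is not lost. Against that, protocol 9.1.1.2 sends a subject who stops study drug to the discontinuation visit, so the treatment reading is the more natural one. The ambiguity itself needs settling.

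Derivation rules sit in separate programming documents (SAP section 9) and may resolve some of this. SAP 5.3.3 plans no statistical comparison, and the estimated effect on PFS is slight. All of this limits the size of the problem. It does not remove the negative DOR in case 2, which follows from the SAP's own text when the CT is done after stopping and no other row takes precedence.

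**Conclusion.** The point holds in a limited form. When the discontinuation CT is done after treatment stops and no other row takes over, the SAP as written uses it as an event if it shows PD and leaves it out of the censoring date if it does not. The loss for an affected subject is nominally up to 8 weeks, or 12 weeks after Week 32. A response first seen on that CT gives a negative DOR. A subject with no other post-baseline scan has a PFS of zero, a negative PFS, or 1 day, depending on an unstated choice of row.

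How many subjects this touches cannot be derived from the documents; the 6% to 19% above rests wholly on assumed PFS and stopping rates and should not be read as a forecast for this trial. The expected shift in PFS estimates is small. DOR is more exposed because few responders contribute. The conclusion assumes that discontinuation means stopping study treatment and that no unseen programming rule overrides the table.

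**What to change.** In SAP 5.4.2:

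1. Change the end date in this row to *date of last evaluable tumor assessment without PD, up to and including the discontinuation assessment and before any new anticancer treatment*.
2. State that discontinuation means the last dose of study treatment.
3. Set the order of precedence between rows.
4. Make first dose (PFS) or first response (DOR) the earliest possible end date.

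No new data are needed. The cost is a small programming change and an SAP revision. SAP Version 2.0 (31 May 2022) already postdates the 02 Dec 2020 cut-off for centrally reviewed images, so the change should be assessed for impact and described in the clinical study report, as protocol 9.7.5 requires.

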### 5.4.3 Other Efficacy Analyses

Not applicable.

## 5.5 Pharmacokinetic, Pharmacodynamic, Pharmacogenomic, and Other Biomarker Analyses

### 5.5.1 Pharmacokinetic Analyses

The Safety Analysis Set will be used for individual tazemetostat plasma concentration listings. The Pharmacokinetic Analysis Set will be used for summaries of tazemetostat plasma concentrations. The data in patient with dose-reduction/interruption will not be included on calculation of summary statistics. If any subject forget the study drug administration within 3 days before each blood collection for PK analysis, the data will not be included in the summary statistics.

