9.1.1.2 Treatment Phase

The Treatment Phase consists of 28 days/cycle for tazemetostat 800 mg twice daily (BID) oral administration (1600 mg total daily dose) on a continuous basis and lasts until discontinuation of study drug. Subjects will discontinue study drug at the time of disease progression (site evaluation), development of unacceptable toxicity, subject's request to discontinue, withdrawal of consent, or study termination by the sponsor. The subject who discontinues study drug during the Treatment Phase will have a discontinuation visit of the Follow-up Phase.

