9.4.1.1 Tazemetostat Dose Reduction and Interruption Instructions

Dose reduction and interruption for subjects who experience tazemetostat-related toxicity will follow the instructions shown in Table 2. Dose reductions will be based on the previous dose level in order of 600, 400 mg BID (1200 mg, 800 mg total daily dose, respectively). Once the dose is reduced, it cannot be increased at a later date. Any dose adjustment must be discussed with the sponsor or discontinue tazemetostat when toxicities requiring dose reduction occur at the dose of 400 mg BID.

If a subject experiences myeloid malignancy including myelodysplastic syndrome, study treatment should be interrupted and restart (including dose modification)/discontinuation of study treatment should be discussed with the sponsor. If a subject experiences T-cell lymphoblastic lymphoma/T-cell acute lymphoblastic leukemia, study treatment should be discontinued and other actions should be discussed with the sponsor.

Study treatment may be interrupted, if it is required to ensure the safety of a subject experiencing an adverse event that is unrelated to the study drug. In such cases, study treatment should be resumed as soon as possible, at the same dose.

Eisai Confidential Page 36 of 71

Table 2 Tazemetostat Dose Reduction and Interruption Instructions

Tazemetostat-related Toxicity		During Therapy ^d	Dose adjustment ^d
Grade 1 and Tole	erable Grade 2ª	Continue tazemetostat	Maintain dose level
Intolerable Grade 2 ^a and Grade 3 ^b		Interrupt tazemetostat until resolved to Grade ≤1 or baseline ^e	Dose reduction by one dose level
Grade 3 and	ANC ≥0.75×10 ⁹ /L	Continue tazemetostat	Maintain dose level
Grade 4 neutropenia	ANC <0.75×10 ⁹ /L	Interrupt tazemetostat until resolved to ANC>0.75×10 ⁹ /L°	Dose reduction by one dose level
Grade 4 ^c		Interrupt tazemetostat until resolved to Grade ≤1 or baseline ^e	Discuss with the sponsor or discontinue tazemetostat

ANC = absolute neutrophil count.

- c: Laboratory abnormalities judged to be non-life threatening, will be excluded and managed as Grade
- d: Discuss with the sponsor when to consider the dose interruption and adjustment other than instructions.
- e: To minimize the duration of interruption, assessment at least every 7 days is recommended. A delay of tazemetostat for more than 28 days due to any toxicity that is related to the study treatment must be discussed with the sponsor before treatment can be resumed.

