- c: Obtain from the patients who has confirmed tumor EZH2 gene mutation in central laboratory.
- d: Collect demography information described in Section 9.5.1.1.
- e: Blood samples for PK analyses of tazemetostat will be collected in C1D15 and C2D1 predose of first administration.
- f: The data of CT scan/endoscopy before informed consent within 28 days from study drug administration can be used as Screening 2 data if it meets the requirement of the protocol. Perform tumor assessment at Screening 2, every 8 weeks from first study drug administration for first 32 weeks (±1 week, eg, C2D21 to C3D7, C4D21 to C5D7...C8D21 to C9D7), then every 12 weeks (±1 week, eg, C11D21 to C12D7, C14D21 to C15D7...) and discontinuation. The data within 28 days can be used as discontinuation data. If gastrointestinal disease were suspected, endoscopic examination will be performed at Screening 2. If exists, perform when it is required to confirm CR as soon as possible or when clinically indicated.
- g: The data of PET scan before informed consent within 28 days from study drug administration can be used as Screening 2 data if it meets the requirement of the protocol. If positive, perform when it is required to confirm CR as soon as possible or when clinically indicated.
- h: The data of bone marrow examination before informed consent within 42 days from study drug administration can be used as Screening 2 data if it meets the requirement of the protocol. If positive or indeterminate, perform when it is required to confirm CR as soon as possible or when clinically indicated.
- i: Subjects should not take study drug before evaluations are performed, unless specified (except tumor assessments and peripheral blood smear morphology assessment).
- j: On Day 15 of each cycle, peripheral blood smear morphology assessment can be omitted at the discretion of the investigator or subinvestigator, if there was no concern for safety of the subject.
- k: In Cycle 13 or later, visits and assessments on Day 15 can be omitted at the discretion of the investigator or subinvestigator, if there was no concern for safety of the subject.
- 1: Final observation is unnecessary for subjects who meet approved indication and receive commercial tazemetostat.

Eisai Confidential Page 53 of 71

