### 5.6.1 Extent of Exposure

The number of cycles received, duration of treatment, total dose per subject, dose intensity per subject, received dose as percentage of planned starting will be summarized for each disease (cohort) and overall. Number of subjects with dose reductions and dose interruptions will be summarized for each disease (cohort) and overall. As for the subjects with any dose reduction, time to first dose reduction will also be summarized.

The actual dosing transition and duration of both study drug with tumor response is presented using swimmer plot.

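### The PK summary excludes patients with a dose reduction or interruption without tying the event to the sample; read literally, it discards troughs taken before the event

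*SAP*

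**What the plan says.** The sentence at issue is in SAP 5.5.1: "The data in patient with dose-reduction/interruption will not be included on calculation of summary statistics". It names the patient and gives no date, no dose-at-draw condition and no window.

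The sentence after it deals with forgotten doses and does give a window: "If any subject forget the study drug administration within 3 days before each blood collection for PK analysis", the data are left out.

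The sampling schedule is short. Table 5, footnote e, in Protocol 9.5.2.1 reads: "Blood samples for PK analyses of tazemetostat will be collected in C1D15 and C2D1 predose of first administration". No later PK sample is planned. Treatment is open-ended: Protocol 9.1.1.2 describes dosing "on a continuous basis and lasts until discontinuation of study drug".

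Protocol 9.4.1.1 covers both kinds of modification. For a reduction, "Once the dose is reduced, it cannot be increased at a later date". For an interruption because of an unrelated adverse event, "In such cases, study treatment should be resumed as soon as possible, at the same dose".

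**The concern.** A trough measures exposure under the dosing that preceded it. There is a good reason to leave out a trough taken on a reduced dose or around an interruption, because it does not describe the planned 800 mg BID regimen. There is no such reason to leave out a trough taken at full dose because the patient was reduced or interrupted weeks or months later.

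The SAP sentence does not separate these cases. A programmer who takes it literally would flag any patient with a modification at any time and remove all of that patient's concentrations. One who takes it as a rule about each sample would remove only the affected ones. Both could claim to follow the SAP, and they would produce different tables. What is at stake is the number of valid values behind the trough summary at each timepoint.

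**Working it through.** The plan gives no figure for this exclusion, so there is none to reproduce. The check compares the two readings and looks for any text that settles the matter.

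**Inputs**
- Draws per patient: 2, at C1D15 and C2D1 (Protocol 9.5.1.4.1 and Table 5).
- Cycle length: 28 days (Protocol 9.1.1.2), so C2D1 is nominally Day 29, with a visit window of ±3 days.
- A reduced dose is never raised again (Protocol 9.4.1.1), so every draw after a first reduction is on a reduced dose.
- Planned efficacy-evaluable patients: 8 + 13 = 21 (Protocol 9.3).

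**Troughs kept under each reading**, assuming both were drawn and no dose was missed in the 3 days before each:

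| First modification | Literal, by patient | By sample |
|---|---|---|
| After C2D1 | 0 of 2 | 2 of 2 |
| Between the draws | 0 of 2 | C1D15 kept; C2D1 excluded after a reduction, or judged by the look-back window after an interruption |
| Before C1D15 | 0 of 2 | Neither after a reduction; judged by the look-back window after an interruption |

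In the first row the literal reading discards 2 − 0 = 2 unaffected troughs per patient. In the second it discards at least 1.

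**Does other text supply the timing?**
- Protocol 9.7.1.7.1 asks for a summary by timepoint and contains no such exclusion.
- SAP 5.5.1.1 describes summaries for all subjects and for those sampled 8 to 16 hours after dosing. It gives no timing for modifications.
- SAP 5.6.1 states: "Number of subjects with dose reductions and dose interruptions will be summarized for each disease (cohort) and overall". This count has no time limit.
- SAP 7 lists the added 95% intervals and subgroup analyses, not this exclusion.
- SAP 8.1 covers the quantification limit, anomalous values and digits only.
- SAP 5.3.5 and the opening of SAP 8 leave data decisions to the time before database lock. SAP 9 and 11 refer to separate specifications and table shells.

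None of these gives a time relation.

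**Scale, for illustration only.** The documents give no rate or timing of modifications in this study. Let k be the number of patients first modified after C2D1, and let the 21 planned patients stand in for the PK Analysis Set. Scheduled troughs are 21 × 2 = 42. Discarded troughs are 2k, n per timepoint is 21 − k, and the share lost is k/21.

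| k (assumed) | Troughs discarded | n per timepoint | Share |
|---|---|---|---|
| 1 | 2 | 20 | 4.8% |
| 3 | 6 | 18 | 14.3% |
| 5 | 10 | 16 | 23.8% |
| 8 | 16 | 13 | 38.1% |

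These rows show how the literal rule scales. They do not estimate what happened in the trial.

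**The case against.** The strongest reply is that the literal reading is not the only one. The sentence does not say that a modification at any time counts. It governs summaries made by timepoint, so it can mean a patient who is reduced or interrupted at that timepoint. The forgotten-dose sentence is equally loose about which data it drops, yet it clearly concerns the collection in question. A summary over all subjects also fits poorly with removing whole patients for later events. The exposure counts in SAP 5.6.1 cover the whole treatment period by their nature and say little about PK handling. The operative rule may sit in specifications that are not public.

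Much of this stands. A sample-level intent is plausible, and actual loss of troughs cannot be established from these documents. What remains is that no text states the sample-level rule, and the literal wording gives the worse result.

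Three stronger inferences are tempting and should not be drawn:
- **Most modifications fall after sampling.** For a patient treated to Week 56, 56 × 7 = 392 days, of which 392 − 28 = 364 (93%) follow a nominal C2D1 draw. That is a share of treatment days. Without the timing of modifications it does not say how many patients are affected.
- **The summary is biased downward** because patients with higher exposure are modified more often. The documents give nothing on exposure and modification in this study, so no bias is claimed.
- **The table will change between data cuts.** A literal rule would allow this if the summary were rerun on later data, but nothing in the documents says that it will be.

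**Conclusion.** The point holds as a minor one. The exclusion is worded by patient, with no time relation to the sample. Followed literally, it removes full-dose troughs because of events that came later and cannot have affected them: both troughs for a patient first modified after C2D1, and the C1D15 trough for one first modified between the draws. This rests on both samples having been drawn with no missed dose in the preceding 3 days.

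The number of such patients is unknown, and so is the total loss. PK is an exploratory objective, the summary is descriptive, n is reported, and individual concentrations stay in the listings. ORR, PFS, DOR, TTR and safety are untouched. The documents do not show that valid data were in fact discarded. They show a rule that permits it and that can be put right at almost no cost.

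**What to change.** Replace the sentence in SAP 5.5.1 with a rule for each sample:
- Exclude a concentration from the summary only if the subject was on a reduced dose at that draw, or had dosing interrupted at the draw or within a stated look-back window before it.
- Have the sponsor specify that window and justify it from the drug's PK. The 3-day window for forgotten doses should not be carried over by default. Protocol Table 2 contemplates treatment delays of more than 28 days, and nothing in the documents shows that 3 days of resumed dosing restores a representative trough.
- Keep all samples taken before the first modification.
- Report the number excluded, with reason, at each timepoint.

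The cost is one or two SAP sentences and minor programming. No new data are needed. Protocol 9.4.9 already collects dosing dates and doses, and Protocol 9.5.1.4.1 collects actual sampling times. SAP 5.6.1 already derives the timing of reductions: "As for the subjects with any dose reduction, time to first dose reduction will also be summarized". If a sample-level rule was intended all along, the edit only records it. It changes no dosing or other clinical rule.
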